11.5. Cohorts for analyses

The following study cohorts will be evaluated.

11.5.1. All enrolled set

All subjects who will sign the inform consent and for whom a subject number is assigned.

11.5.2. Total vaccinated cohort

The total vaccinated cohort (TVC) will include all subjects with at least 1 documented study vaccine administration, with respect to the vaccine actually administered:

- A **safety** analysis based on the TVC will include all subjects with at least one vaccine dose administered and who provided safety data.
- An **immunogenicity/efficacy** analysis based on the TVC will include all vaccinated subjects for whom immunogenicity/ efficacy data are available.
- An **efficacy** analysis based on the TVC will include all subjects for whom at least one dose was administered.

In subjects receiving only one dose the efficacy endpoint is the number of moderate or severe AECOPD (any cause), occurring within a period starting from Day 90 and lasting for 1 year (until study conclusion).

The TVC analysis will be performed per treatment actually administered at Dose 1.

11.5.3. Modified total vaccinated cohort

The modified total vaccinated cohort (mTVC) will include all subjects with 2 documented study vaccine administrations with respect to the vaccine actually administered.

The primary efficacy analysis will be performed on the mTVC.

11.5.4. Per-protocol set for analysis of immunogenicity

The per-protocol set (PPS) for immunogenicity will include all subjects in the TVC:

- Who met all eligibility criteria.
- For whom the administration of the vaccines was according to protocol.
- Who complied with the vaccination schedule, as specified in [Table 8](#).
- Who received the study vaccines according to protocol procedures.
- Who did not receive a concomitant medication/ product leading to elimination from the PPS (per-protocol) analysis for immunogenicity (see Section [7.6.2](#)) up to the 1 month post--Dose 2 visit (Day 91).
- Who did not present an intercurrent medical condition leading to elimination from the PPS analysis for immunogenicity (see Section [7.7](#)), up to the 1 month post--Dose 2 visit (Day 91).
- Who complied with the blood sample timings as specified in [Table 8](#), at the 1 month post-Dose 2 visit (Day 91).
- For whom post-vaccination immunogenicity results are available for at least 1 assay.

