7.6.1. Recording of concomitant medications/products and concomitant vaccinations

The following concomitant medication(s)/product(s)/vaccine(s) must be recorded in the eCRF.

- All concomitant vaccines/medications/products, except vitamins and dietary supplements, administered during the entire study period following the first dose of study vaccine (Day 1 to Day 451).
- Prophylactic medication (i.e. medication administered in the absence of ANY symptom and in anticipation of a reaction to the vaccination).

E.g. an anti-pyretic is considered to be prophylactic when it is given in the absence of fever and any other symptom, to prevent fever from occurring [fever is defined as temperature $\geq 37.5^{\circ}\text{C}/99.5^{\circ}\text{F}$]. The preferred location for measuring temperature in this study will be the oral cavity or the axilla.

- Any concomitant medications/products/vaccines listed in Section 7.6.2.
- Any concomitant medications/products/vaccines relevant to a SAE/pIMD to be reported as per protocol or administered during the study period for the treatment of a SAE /pIMD. In addition, concomitant medications relevant to SAEs and pIMD need to be recorded on the expedited Adverse Event report.
- Any receipt of influenza vaccine up to 1 year before the first dose of study vaccine.
- Any receipt of pneumococcal vaccine at any time before the first dose of study vaccine. Approximate timing of receipt should be recorded.

7.6.2. Concomitant medications/products/vaccines that may lead to the elimination of a subject from per-protocol analyses for immunogenicity

The use of the following concomitant medications/products/vaccines will not require withdrawal of the subject from the study but may determine a subject's evaluability in the per-protocol analysis for immunogenicity. See Section 11.5 for cohorts to be analysed.

- Any investigational or non-registered product (drug or vaccine) other than the study vaccine used during the study period.
- A vaccine not foreseen by the study protocol administered during the period starting 30 days before and ending 30 days after each dose of vaccine*, with the exception of any influenza, pneumococcal vaccines or other routinely recommended vaccine which may be administered ≥ 15 days preceding or following any dose of study vaccine.

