* In case an emergency mass vaccination for an unforeseen public health threat (e.g.: a pandemic) is organised by the public health authorities, outside the routine immunisation program, the time period described above can be reduced if necessary for that vaccine provided it is licensed and used according to its Prescribing Information and according to the local governmental recommendations and provided a written approval of the Sponsor is obtained.

- Immunoglobulins or any blood products administered at any time during the study period.
- Immunosuppressants or other immune-modifying drugs administered chronically (i.e. more than 14 days) at any time during the study period (e.g. methotrexate). Use of corticosteroids is allowed as per local treatment recommendations.

7.6.3. Concomitant medications/ products/ intervention that may lead to the elimination of a subject from the per-protocol analysis for efficacy

In addition to the concomitant medications/ products/ vaccines described in the Section 7.6.2, the use of the following medications/ products/ intervention will not require withdrawal of the subject from the study but may determine a subject's evaluability in the per-protocol analysis for efficacy.

- Underwent lung transplantation/ lung resection surgery at any time during the entire study period.
- Chronic use of antibiotics at any time during the entire study period.

7.7. Intercurrent medical conditions that may lead to elimination of a subject from per-protocol analyses

At each study visit subsequent to the first vaccination, it must be verified if the subject has experienced or is experiencing any intercurrent medical condition. If it is the case, the condition(s) must be recorded in the eCRF.

Subjects may be eliminated from the per-protocol cohort for immunogenicity and efficacy if, during the study, they incur a condition that has the capability of altering their immune response or are confirmed to have an alteration of their initial immune status.

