11.9. Analysis of immunogenicity

The analysis will be performed on the immunogenicity ATP (per-protocol) cohort. If the percentage of vaccinated subjects with serological results excluded from the ATP cohort for analysis of immunogenicity is more than 10%, a second analysis will be performed on the TVC.

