11.9.1. Within groups assessment

Humoral immune response

For each group and at each timepoint during which blood samples are collected for humoral immune response (at Day 1, Day 31, Day 61, Day 91, Day 271 and at Day 451), and for each component (PD, PE, PilA and UspA2), the following will be computed:

- Seropositivity rate (i.e, percentage of seropositive subject) and the associated exact 95% CI
- GMCs and the associated 95% CI

The distribution of antibody concentrations will be investigated using Reverse Cumulative Curves.

A seropositive subject is a subject whose antibody concentration is greater than or equal to the assay cut-off value, as specified in [Table 10](#).

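### The per-protocol set for immunogenicity stops its product and condition eliminations at Day 91 but is used for antibody results at Day 271 and Day 451, a limit not reconciled with the study-long windows elsewhere in the protocol

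*Protocol*

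**What the plan says.** Section 11.5.4 defines the per-protocol set (PPS) for immunogenicity. Two of its criteria, on concomitant products (Section 7.6.2) and on intercurrent conditions (Section 7.7), carry the limit "up to the 1 month post--Dose 2 visit (Day 91".

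Section 11.9 assigns the analysis to that one set: "The analysis will be performed on the immunogenicity ATP (per-protocol) cohort". Section 11.9.1 asks for seropositivity rates and GMCs "at Day 1, Day 31, Day 61, Day 91, Day 271 and at Day 451". The protocol defines no other per-protocol set for the two late timepoints.

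Section 7.6.2 lists what "may determine a subject's evaluability in the per-protocol analysis for immunogenicity". Three of its four items run through the study:

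- "Any investigational or non-registered product (drug or vaccine) other than the study vaccine used during the study period"
- "Immunoglobulins or any blood products administered at any time during the study period"
- drugs that suppress or modify immunity, where they are "administered chronically (i.e. more than 14 days) at any time during the study period"

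Section 7.7 allows elimination from both the immunogenicity and efficacy sets for a condition, incurred during the study, that can alter the immune response.

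**The concern.** The same products and conditions have two different windows, and the shorter one governs a set whose results extend 360 days past it. A subject given immunoglobulin, or started on a long course of an immunosuppressant, on Day 120 has an exposure that Section 7.6.2 names because it can affect the antibody measurement. Under Section 11.5.4 that subject still contributes to the per-protocol GMC and seropositivity rate at Day 271 and Day 451.

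Antibody concentrations at those days are named secondary endpoints (Section 11.2) and the only scheduled humoral readings after Day 91. Passively acquired antibody would push levels up and immunosuppression would push them down. A reader would expect a set labelled per-protocol to exclude both.

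**Working it through.** No sample size, power or alpha figure is involved. The check sets the sections side by side.

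**Windows for the immunogenicity PPS**

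| Item | Section 7.6.2 or 7.7 | Section 11.5.4 |
|---|---|---|
| Investigational products | study period | up to Day 91 |
| Immunoglobulins, blood products | any time in the study | up to Day 91 |
| Chronic immunosuppressants | any time in the study | up to Day 91 |
| Unplanned vaccines | 30 days either side of each dose | up to Day 91 |
| Immune-altering conditions | during the study | up to Day 91 |

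The vaccine row shows that Section 7.6.2 does use a dose-related window where one is wanted. With Dose 2 on Day 61, 61 + 30 = Day 91, so that row agrees with Section 11.5.4. The other four rows do not.

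**Reach of the gap**

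- Follow-up from Day 1 to Day 451: 451 - 1 = 450 days.
- Follow-up after the limit: 451 - 91 = 360 days.
- Share with no product or condition elimination for this set: 360 / 450 = 80%.
- Humoral timepoints after the first dose: Days 31, 61, 91, 271 and 451. Two of the five fall after the limit.

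**Comparison with the efficacy PPS.** Section 7.6.3 takes over the whole 7.6.2 list and adds to it. Section 11.5.5 refers to 7.6.3 without any Day 91 limit. So immunoglobulin on Day 120 may take a subject out of the per-protocol efficacy analysis, yet leaves the same subject in the per-protocol antibody results at Days 271 and 451.

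**Does the fallback help?** Section 11.9 repeats the analysis on the total vaccinated cohort if more than 10% of vaccinated subjects with serological results are excluded. That cohort includes every vaccinated subject with data, so the subjects in question are in it too.

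**Size.** If a fraction f of a group has its concentration multiplied by k, the mean log concentration moves by f × log k and the GMC is multiplied by k^f. The protocol gives neither f nor k, so no shift can be calculated from it.

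**The case against.** The strongest reply is that Sections 7.6.2 and 7.7 are permissive. They say that such subjects may be affected, 7.6.2 sends the reader to Section 11.5 for the cohorts, and 11.5.4 then fixes the operative window. One study-long list could serve both per-protocol sets, with 11.5.4 deliberately shortening it for immunogenicity. This stands to the following extent: a reader might infer that the protocol itself declares these subjects non-evaluable and then admits them, and the documents do not support that. What remains is an unexplained difference in windows. The Day 91 limit suits the Day 91 comparison, but nothing says why it should also govern samples taken 180 and 360 days later.

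A reader might extend the point to sample timing at Visits 6 and 8, since 11.5.4 checks timing only at Day 91 ("Who complied with the blood sample timings as specified in" Table 8). There is no conflict there. Table 8 footnote 1 ties eligibility for this set only to the Visit 1 to Visit 3 and Visit 3 to Visit 4 intervals, and 11.5.4 agrees. For the same reason, removing a subject with a late Day 91 sample from the earlier timepoints follows a stated rule and is not an error.

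A reader might also want a number. If 10% of a group were affected with a tenfold rise, the GMC would rise by 26% (10^0.10 = 1.26). Neither input has a source in the protocol. Section 5.3 excludes planned immunoglobulins, blood products and investigational products, as well as prior chronic immunosuppressant use, and 7.6.2 allows corticosteroids. All this suggests that such exposures would be uncommon.

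Lastly, timepoint-specific sets are often left to the statistical analysis plan, which is not at hand. Here, however, the protocol states one set with one explicit limit. A different rule in that plan would be a change, which Section 11.12 requires to be described and justified in the study report.

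**Conclusion.** The point holds as an unreconciled rule. Followed literally, Section 11.5.4 keeps subjects with a 7.6.2 or 7.7 elimination reason arising after Day 91 in the per-protocol antibody results at Day 271 and Day 451. That sits badly with the windows in 7.6.2 and 7.7 and with the treatment of the 7.6.2 list in the efficacy PPS.

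The consequence is limited. The Day 271 and Day 451 results are within-group summaries of a secondary endpoint, and Section 11.11 treats secondary comparisons as descriptive. The only planned GMC ratio between groups is at 1 month post-Dose 2 (Section 11.9.2), where the Day 91 limit fits. The primary efficacy analysis uses the modified total vaccinated cohort and is untouched. The number of subjects affected and the resulting shift cannot be derived from the protocol. The conclusion assumes only that Sections 11.5.4, 11.9 and 11.9.1 are applied as written.

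**What to change.** Amend Section 11.5.4 as follows:

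- Keep the present Day 91 set for results up to and including Day 91 and for the GMC-ratio ANCOVA in Section 11.9.2.
- For Day 271 and Day 451, start from that set and exclude a subject's results from the first 7.6.2 or 7.7 elimination reason arising before the sample in question.
- Align Sections 7.6.2 and 7.7 with this rule so that one window applies to each timepoint. Leave Table 8 footnote 1 as it is.

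No new data are needed. Section 7.6.1 already records concomitant products to Day 451, and Section 7.7 has intercurrent conditions checked at each visit after the first vaccination. The cost is the wording and elimination codes by timepoint, which should be settled before unblinding. The downside is that the number of subjects will differ between timepoints, so each table should show its own denominator.

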11.5.5. Per-protocol set for analysis of efficacy

The PPS for analysis of efficacy will include all subjects in the TVC:

- Who met all eligibility criteria.
- For whom the administration of the vaccines was according to protocol.
- Who complied with the vaccination schedule, as specified in [Table 8](#).
- Who received the study vaccine according to protocol procedures.
- Not having received a medication/ product/ vaccine that may lead to elimination from the PPS (per-protocol) analysis for efficacy (see Section [7.6.3](#)).

In addition, for the Bacteriological efficacy endpoints:

- For whom the sputum sample results are available.

11.5.6. Full Analysis set (FAS)

The FAS will include all randomized subjects who will receive at least 1 vaccine administration. As per intention-to-treat principle, a subject in the FAS will be analysed “as randomized” (i.e. according to the vaccine a subject was planned to receive irrespectively of his/her real exposure).

11.6. Derived and transformed data

The study groups will be defined by treatment actually administered at Dose 1.

Demography

- For a given subject and a given demographic variable, missing measurement will not be replaced.

Efficacy – Clinical Endpoint

- For a given subject and a given efficacy measurement, missing or unevaluable measurements will not be imputed. The missing endpoint and censoring are supposed to occur independently, and the pattern of the missing is assumed to be Missing Completely at Random (MCAR) or Missing At Random (MAR) only.
- The number of AECOPD occurring during the 1 year follow-up period starting 1 month post-Dose 2 will be used to describe vaccine efficacy (VE). Exacerbation rate reported during this period will be calculated for each subject. The number of exacerbations during the 1-year follow-up period will be imputed for subjects withdrawing from the study to provide an estimate of the number of exacerbations over the follow-up period. This calculation will only be performed for purposes of reporting summary statistics since the modelling of exacerbations takes into account the number of exacerbations and the time of follow-up for each subject.
- The number of AECOPD occurring from enrolment up to 1 month post-Dose 2 will be used as ‘baseline’ value. No difference between vaccine and placebo is expected in this period.
- The calculation of exacerbation rate will be based on follow-up period intervals to avoid obtaining high imputed rates if a subject withdrew very early in the follow-up period after experiencing an exacerbation. Since treatment courses for moderate/severe exacerbations are $\leq 2 - 4$ weeks when appropriate, calculated numbers of exacerbations for subjects withdrawing from the study will be based on 4-week intervals of the follow-up period. For subjects followed for less than 1 year, the number of exacerbations during the 1-year follow-up period will be calculated by multiplying the number of exacerbations experienced by the subject by 13 and dividing by the number of 4-week periods the subject was followed up [[Stockley, 2006](#)]:

Number of exacerbations per year = Number of exacerbations * 13 /Number of 4-week treatment period intervals.

Safety

- For solicited symptoms, missing or unevaluable measurements will not be replaced. Therefore the analysis of the solicited symptoms based on the TVC will include only subjects/doses with documented safety data (i.e., symptom screen/sheet completed).
- For the unsolicited symptoms and concomitant medications/ products/ vaccinations, all vaccinated subjects will be considered and subjects who miss reporting symptoms/concomitant medications/ products/ vaccinations will be treated as subjects without unsolicited symptoms or concomitant medications/ products/ vaccinations, respectively.

Efficacy – Bacteriological Endpoint

- For a given subject and a given bacteriological measurement, missing or unevaluable measurements will not be imputed.
- Subjects who did not have any sputum collected or have missing measurements at all AECOPD (if at least 1 AECOPD occurred) will not be taken into account for the NTHi and/or Mcat-associated AECOPD analyses.

Immunogenicity

- Calculation of the GMCs will be performed by taking the anti-logarithm in base 10 (anti-log10) of the mean of the log10 concentration transformations.
- Antibody concentrations below the assay cut-off will be given an arbitrary value of half the assay cut-off for the purpose of geometric mean concentration (GMC) calculation.
- A seronegative subject is defined as a subject whose antibody concentration is below the assay cut-off value (i.e. the ELISA lower limit of quantification).
- A seropositive subject is defined as a subject whose antibody concentration is greater than or equal to the assay cut-off value (i.e. the ELISA lower limit of quantification).
- For a given subject and the analysis of a given immunogenicity measurement, missing or unevaluable measurements will not be replaced.

CMI

- The frequency of CD4⁺ T-cells producing two or more markers (such as CD40 Ligand (CD40L), interleukin (IL)-2, IL-13, IL-17, interferon gamma (IFN- γ), tumour necrosis factor alpha (TNF- α), upon in vitro stimulation with the antigen (induction condition) is presented per million of CD4⁺ T cells for the analysis and in percent for the graphical representation.

- The frequency of antigen-specific CD4⁺ T-cells for each individual subject is calculated as the difference between the frequency of CD4⁺ T-cells producing at least 2 cytokines among IFN- γ , IL-2, IL-13, IL-17, TNF- α and/or CD40L, upon *in vitro* stimulation with the antigen (induction condition) minus the frequency of CD4⁺ T-cells producing at least 2 cytokines upon *in vitro* stimulation in medium only (background condition).

$$Freq_{Induction}^{2+} = \frac{n_{Induction}^{2+} - n_{background}^{2+}}{1000000} \quad Log_e(Freq_{Induction}^{2+}) = Log_e\left(\frac{n_{Induction}^{2+} - n_{background}^{2+}}{1000000}\right)$$

$n_{Induction}^{2+}$ = Number of antigen-specific CD4⁺ T-cells expressing two or more cytokines.

- The frequency of CD4⁺ T-cells expressing a marker (such as interleukin (IL)-2, IL-13, IL-17, interferon gamma (IFN- γ), tumour necrosis factor alpha (TNF- α) upon *in vitro* stimulation with the antigen (induction condition) is presented per million of cells for the analysis and per hundred cells for the graphical representation.
- Values less or equal to zero will be set to 1 for the purpose of the analysis.
- The Geometric Mean (GM) frequency calculations are performed by taking the anti-log of the mean of the log frequency transformations.

HRQOL

- The CAT index will be derived as the sum of the ratings recorded for each of the eight individual items. Each of these items has 6 possible scores (0, 1, 2, 3, 4 or 5), leading to a range of 0 to 40 for CAT score.
- The SGRQ-C score will be grouped in total scores and by three component scores: Symptoms, Activity, Impacts. Score are assigned following the SGRQ-C Manual.

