6.2.2.2. Treatment allocation to the subject

The treatment numbers will be allocated by dose.

6.2.2.2.1. *Study group and treatment number allocation*

The target will be to enrol approximately 600 eligible subjects who will be randomly assigned to two study groups in a (1:1) ratio (approximately 300 subjects in each group).

Allocation of the subject to a study group at the investigator site will be performed using a randomisation system on internet (SBIR). The randomisation algorithm will use a minimisation procedure accounting for age (40 - 59 years or 60 - 80 years), number of moderate/ severe AECOPD in the previous year (< 2 or ≥ 2), GOLD grade (GOLD 2, GOLD 3 or GOLD 4) and country. Minimisation factors will have equal weight in the minimisation algorithm.

Details on the minimisation algorithm are reported in the statistical analysis plan.

At Visit 1, before administration of vaccine Dose 1 to eligible subjects who signed and dated the ICF at the Screening Visit, the study staff in charge of the vaccine administration will access SBIR. Upon providing the subject's age category (40 - 59 years or 60 - 80 years), number of moderate/ severe AECOPD in the previous year, his/ her GOLD grade and subject identification number, the randomisation system will determine the study group and will provide the treatment number to be used for the first dose.

The number of each administered treatment must be recorded in the eCRF on the Vaccine Administration screen.

When SBIR is not available, please refer to the SBIR user guide or the Study Procedures Manual (SPM) for specific instructions.

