6.2.2.2.2. Treatment number allocation for subsequent doses

For each dose subsequent to the first dose, the study staff in charge of the vaccine administration will access SBIR, provide the subject identification number, and the system will provide a treatment number consistent with the allocated study group.

The number of each administered treatment must be recorded in the eCRF on the Vaccine Administration form/screen.

When SBIR is not available, refer to the SBIR user guide or the SPM for specific instructions.

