11.10. Analysis of safety

The analysis will be performed on the TVC.

The percentage of subjects with at least one **local AE** (solicited and unsolicited), with at least one **general AE** (solicited and unsolicited) and with any AE during the 7-day (Day 1 – Day 7) or the 30-day (Day 1 – Day 30) follow-up period will be tabulated after each vaccination and overall with exact 95% confidence interval (CI). The same computations will be done for Grade 3 AEs, for related AEs and for Grade 3 related AEs.

The percentage of subjects/doses reporting each individual solicited local (any grade, Grade 3) and general (any grade, Grade 3, related, Grade 3 related) AE during the 7-day (Day 1 to Day 7) follow-up period will be tabulated for each group as follows:

- Overall, the percentage of subjects with the symptom and its exact 95% CI.
- Overall, the percentage of doses with the symptom and its exact 95% CI.

- Per study vaccine dose, the percentage of subjects with the symptom and its exact 95% CI.

The exact 95% CIs will be calculated assuming independence between doses. For fever, additional analyses will be performed by 0.5°C increments.

The verbatim reports of **unsolicited** symptoms will be reviewed by a physician and the signs and symptoms will be coded according to the MedDRA Dictionary for Adverse Reaction Terminology. Every verbatim term will be matched with the appropriate preferred term (PT). The percentage of subjects with unsolicited symptoms during the 30-day follow-up period after any study vaccine dose with its exact 95% CI will be tabulated by group and by MedDRA PT. Similar tabulation will be done for the percentage of doses, for Grade 3 unsolicited symptoms, for unsolicited symptoms that resulted in a medically attended visit, for Grade 3 and causally related unsolicited symptoms and for unsolicited symptoms causally related to vaccination.

The number of subjects who experienced any **pIMD** or any **SAE** from first vaccination up to 12 months post-Dose 2 will be reported.

The number of subjects who experienced any **AE leading to study withdrawal**, from first vaccination up to study conclusion, or any **SAE related to study participation of concurrent GSK medication/ vaccination**, during the entire study period, will be reported.

Pregnancy from first vaccination up to study end for each female subject and pregnancy outcomes will be described in detail.

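### Safety groups follow the product given at Dose 1 only, so a subject given placebo first and the adjuvanted vaccine in error at Dose 2 stays in the placebo column

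*Protocol*

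**What the plan says.** Two sections of the protocol give the same grouping rule. Section 11.6 states "The study groups will be defined by treatment actually administered at Dose 1", and Section 11.5.2 states "The TVC analysis will be performed per treatment actually administered at Dose 1". The TVC itself is introduced as the as-treated set: it takes in subjects "with at least 1 documented study vaccine administration, with respect to the vaccine actually administered".

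Section 11.10 ties safety to that set: "The analysis will be performed on the TVC". Its solicited-event tables give a percentage of subjects overall, a percentage of doses, and "Per study vaccine dose, the percentage of subjects with the symptom and its exact 95% CI". For longer-window events, the number of subjects with any pIMD or SAE "from first vaccination up to 12 months post-Dose 2 will be reported".

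On supply, Section 6.2.2.2 says "The treatment numbers will be allocated by dose". At the second dose the site goes back to the internet randomisation system (SBIR), and under Section 6.2.2.2.2 "the system will provide a treatment number consistent with the allocated study group".

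**The concern.** The TVC exists to describe what subjects actually received; the full analysis set in Section 11.5.6 already gives the as-randomised view. The grouping rule checks exposure at only one of the two doses. If the wrong product is given at Dose 2 alone, the rule does not see it.

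The sequence that matters is placebo, then vaccine. That subject has been exposed to the antigens and the adjuvant but remains in CONTROL throughout. Section 9.3.3.2.2 treats all solicited reactions as causally related to vaccination, so a reaction to the vaccine would appear as a vaccination-related reaction in the placebo column. Later unsolicited AEs, SAEs and pIMDs would go to the same column. Vaccine-induced autoimmune disease is the only vaccine-specific risk listed in Section 1.4.1, so this is the kind of event for which an as-treated table should not count an exposed subject as unexposed.

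**Working it through.** No stated figure is at issue, so there is nothing in the protocol to reproduce. The check has two parts: what the rule does in each sequence, and how large the effect could be.

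**Reading the sections together.** Sections 11.5.2 and 11.6 fix the group at Dose 1, and Section 11.10 uses the TVC. No current section regroups Dose 2 events by the product given at Dose 2.

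| Given at Dose 1, then Dose 2 | Group under the rule | Dose 2 per-dose and percentage-of-doses tables | Subject-level AE, SAE and pIMD tables |
|---|---|---|---|
| Placebo, then vaccine (error) | CONTROL | Vaccine reactions counted under placebo | Vaccine-exposed subject counted under placebo |
| Vaccine, then placebo (error) | Vaccine | Placebo response counted under vaccine (dilution) | Correct: the subject has been exposed to vaccine |

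For Dose 1 tables the rule is right in both rows.

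**Effect on one percentage.** Assume that about 285 of about 300 control subjects receive Dose 2, and that 0 to 1% of Dose 2 administrations are wrong. The protocol gives neither figure. The number misdosed is then 0 to 3 (1% of 300 = 3). One misplaced reaction moves the control percentage by up to 1/285 = 0.35 points.

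**Effect on the Dose 2 difference between groups.** Let q be the share of each group given the wrong product at Dose 2, and let p_v and p_c be the true reaction rates after vaccine and placebo. Grouping by Dose 1 gives

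- vaccine column: (1 − q)p_v + q·p_c
- control column: (1 − q)p_c + q·p_v
- difference: (1 − 2q)(p_v − p_c)

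The difference shrinks by the fraction 2q. With 300 per group, equal errors in both groups and two assumed pairs of reaction rates:

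| Errors per group | q | Difference shown, 70% v 20% (true 50.0 points) | Difference shown, 50% v 10% (true 40.0 points) | Relative loss (2q) |
|---|---|---|---|---|
| 1 | 0.33% | 49.7 | 39.7 | 0.7% |
| 3 | 1% | 49.0 | 39.2 | 2% |
| 6 | 2% | 48.0 | 38.4 | 4% |
| 15 | 5% | 45.0 | 36.0 | 10% |

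Grouping each dose by the product given at that dose restores the true difference in every row.

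**Chance of a misplaced pIMD.** The expected number is (misdosed controls) × (pIMD risk per subject). At the upper end of the assumptions, with 3 misdosed controls and 2 cases per arm of about 300, it is 3 × 2/300 = 0.02. With 1 misdosed control and 1 case per arm it is 1 × 1/300 = 0.003. With no errors it is zero.

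**Interim safety review.** Section 9.10.2 plans a review when about 60 subjects are one month past Dose 2. With about 30 per group (assumption), one subject is 1/30 = 3.3 points, if that review uses the same grouping. The protocol does not say whether it does.

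**The case against.** The best defence is that the rule is clear, is stated the same way twice, and gives each subject one group. Display of rare mixed-exposure subjects could be left to the SAP. A wrong product at Dose 2 would have to get past several controls: SBIR issues a number matching the allocated group, replacement vials must match the randomised formulation (Section 7.4), and an unblinded team prepares two products that look different, only one of which needs reconstitution (Section 6.3). Such an event would also be traceable. Treatment numbers are recorded at each dose, erroneous administration is among the contributing factors considered for each SAE, pIMDs are reported individually within 24 hours, and the internal safety committee sees unblinded data.

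Most of this stands and limits the size of the point. It does not remove it. SBIR controls which number is issued, not what is injected, and an as-treated rule is needed only for the cases where something went wrong. Nor is this simply an SAP detail: the protocol states the rule, and under Section 11.12 a departure from it would have to be described and justified in the study report.

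A reader might go further in three ways that the documents do not support.

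- That every event after a wrong Dose 2 is miscounted, in either direction. It is not: pIMDs and SAEs are counted per subject from first vaccination, so a vaccine-then-placebo subject belongs in the vaccine group.
- That a pIMD imbalance is at real risk of being reversed. One misplaced case could turn 1 versus 0 into 0 versus 1, but the expected number of such cases is about 0.02 even at the upper assumptions.
- That Section 11.5.2 contradicts itself. Its opening words are general, and the later sentence makes them specific to Dose 1.

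**Conclusion.** The point holds in a limited form and carries minor weight. For a subject given placebo and then vaccine in error, the stated rule gives a wrong as-treated result in the Dose 2 reactogenicity tables and in the later AE, SAE and pIMD tables. For the reverse error, only the Dose 2 per-dose reactogenicity tables are affected.

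The size rests on assumptions, because the protocol gives no error rate and no expected reaction rates. With 0 to 3 misdosed controls, each moves a Dose 2 percentage by up to about 0.35 points. With 3 errors in each group, the Dose 2 difference loses about 2% of its value. The effect on common reactions is negligible unless errors are frequent. Efficacy, alpha and power are not touched.

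**What to change.** Add to Sections 11.5.2 and 11.6, for safety tables only:

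- Per-dose and percentage-of-doses tables are grouped by the product given at that dose. For Dose 1 this is the present rule.
- In subject-level tables (overall solicited events, unsolicited AEs, SAEs, pIMDs), a subject who received at least one dose of investigational vaccine is placed in the vaccine group, in both numerator and denominator.
- Subjects who received different products at the two doses are listed separately, with the timing of each event relative to each dose. This is needed because the second rule also moves a placebo-then-vaccine subject's events before Dose 2 into the vaccine group.

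Leave the efficacy grouping unchanged. The cost is a few sentences and one listing, settled before unblinding. If no dosing errors occur, every table is the same as under the present rule.
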